## 1. SYNOPSIS

**Protocol Number:**

**ATI-50002-AAB-201**

**Protocol Title:**

An Open-Label Pilot Study of the Safety, Tolerability and Efficacy of ATI-50002 Topical Solution Administered Twice-Daily in Adult Subjects with Eyebrow Loss due to Alopecia Areata, Alopecia Universalis or Alopecia Totalis

**Sponsor:**

Aclaris Therapeutics, Inc.

**Phase of Development:**

Phase 2

**Study Drug Description:**

ATI-50002 Topical Solution 0.46%

**Study Objective:**

The main objective of this study is to assess the safety, tolerability and efficacy of ATI-50002 Topical Solution 0.46% in subjects with unilateral or bilateral loss of eyebrow hair due to alopecia areata (AA), alopecia universalis (AU) or alopecia totalis (AT).

**Study Design:**

This is an open-label study which will be conducted at 1 to 2 sites.

Subjects will be required to have a clinical diagnosis of AA, AU or AT with unilateral or bilateral loss of eyebrow hair with a duration of the current episode of at least 6 months, but not more than seven years. A total of approximately 12 subjects will apply ATI-50002 Topical Solution 0.46%, to the affected eyebrow(s) twice-daily (BID) for 24 weeks.

After completing Visit 1 (start of the screening period), subjects will be assessed for eligibility to receive study medication.

Subjects will apply study medication to the entire affected eyebrow(s), twice-daily for 24 weeks. The 24-week treatment period will be followed by a 4-week no-treatment follow-up period. Assessment of response to treatment will be performed at Week 4, Week 8, Week 12, Week 16, Week 20, Week 24 and Week 28.

Safety and tolerability will be evaluated throughout the study by assessment of electrocardiograms (ECG), clinical laboratory tests, adverse events and vital signs.

The duration of the study participation is anticipated to be a maximum of 233 days (an up to 28-day screening period, a 169-day treatment period with a 4-day window, a 28-day no-treatment follow-up period with a window of 4 days).

Study visits are:

- Visit 1 (Day -28 to 0): screening; start eligibility assessment period
- Visit 2 (Week 0): initiation of twice-daily study medication application

CONFIDENTIAL

Page 7 of 57

- Visits 3-10 (Weeks 1-24): treatment period
- Visit 11 (Week 28): no-treatment period follow-up; end of study

**Number of Subjects to be Enrolled:**

Approximately 12 subjects will be enrolled in this study.

**Number of Study Sites:**

This study will be conducted at up to 2 sites in the US.

**Inclusion Criteria:**

To be eligible for the study, subjects must fulfill all the following criteria:

1. Subject is at least 18 years of age.
2. Subject has, based on a subject history and clinical examination, a clinical diagnosis of AA, AU or AT with no eyebrow hair in the affected area(s) and no eyebrow regrowth over the previous 6 months. Affected area is defined as the area(s) of eyebrow hair loss identified at Baseline.
3. Subject has a Clinician Eyebrow Assessment score of 0 (No eyebrow hair in the affected area) for at least one eyebrow.
4. Subject has a Subject Eyebrow Assessment score of 0 (No eyebrow hair in the affected area) for at least one eyebrow.
5. Subject has a duration of the current episode of AA, AU or AT with unilateral or bilateral loss of eyebrow hairs (with at least one distinct patch of  $\geq 30\%$  loss of eyebrow hair) for at least 6 months and no more than seven years prior to Visit 1.
6. Subjects who are Women of Childbearing Potential (WOCBP) must have a negative serum pregnancy test at Screening and a negative urine pregnancy test at Baseline and agree to use a highly effective method of birth control for the duration of the study and for 30 days after last study medication application.
7. Subject is non-pregnant and non-lactating and not planning a pregnancy during the duration of the study and for 30 days after the last study medication application.
8. Subject is in good general health and free of any known disease state or physical condition which, in the opinion of the investigator, would interfere with the study requirements or put the subject at undue risk by study participation.
9. Subject is willing and able to follow all study instructions and to attend all study visits.
10. Subjects taking hormonal replacement therapy must have been on the same dose for at least 6 months prior to Visit 1 and must agree to maintain the same dose for the duration of the study and for 90 days after the last study medication application.
11. Subjects taking thyroid replacement therapy must have been on the same dose for at least 6 months prior to Visit 1 and must agree to maintain the same dose for the duration of the study.
12. Subject agrees to refrain from any eyebrow removal (e.g., plucking, threading, etc.) for the duration of the study.

CONFIDENTIAL

Page 8 of 57

13. Subject agrees to refrain from any cosmetic surgery (*e.g.*, piercing, tattooing, etc.), on the treatment areas, for the duration of the study.
14. Subject can comprehend and is willing to sign an Informed Consent Form (ICF).
15. Sexually active male subjects must agree to use a barrier method of contraception from the first application of study medication to at least 30 days after the last application of study medication.

**Exclusion Criteria:**

Any subject who meets one or more of the following criteria will not be included in this study:

- 1) Subject has, in the opinion of the investigator, permanent eyebrow loss attributed to causes other than AA, AU or AT such as overgrooming, or scarring hair loss.
- 2) Subject currently has, or has a history of, skin disease in the eyebrow area (*e.g.*, psoriasis, seborrheic dermatitis, etc.) that, in the opinion of the investigator, would interfere with the study medication application or study assessments.
- 3) Subject currently has, or has a history of, severe, progressive or uncontrolled autoimmune, metabolic, endocrinologic, renal, hepatic, gastrointestinal, pulmonary, cardiovascular, genitourinary (*i.e.*, renal disease), hematological disease, neurologic or cerebral disorders, infectious disease or coagulation disorders that, in the opinion of the investigator, put the subject at undue risk by study participation.
- 4) Subject currently has, or has a history of, proven or suspected systemic or cutaneous malignancy and /or lymphoproliferative disease, other than a history of adequately treated, well healed and completely cleared non-melanoma skin cancers (*e.g.* basal or squamous cell carcinoma) treated successfully at least one year prior to Visit 1.
- 5) Subject currently has evidence of active or latent bacterial infection, including tuberculosis, or viral infections at the time of enrollment or a history of incompletely treated or untreated tuberculosis. Subjects who have completed therapy for latent tuberculosis may participate.
- 6) Subject has a history of serious local infection (*e.g.*, cellulitis, abscess) or a systemic infection, including but not limited to, pneumonia or septicemia, within 12 weeks prior to Visit 1. Subjects on an antibiotic for a nonserious, acute local infection must complete the antibiotic course prior to enrollment in the study.
- 7) Subjects positive for HIV, Hepatitis B or C. Subjects with serologic evidence of Hepatitis B vaccination (HepB surface Ab without the presence of HepB surface Ag) will be allowed to participate.
- 8) Subject currently has or has a known history of herpes zoster or cytomegalovirus (CMV) within 8 weeks prior to Visit 1.
- 9) Subject has a history of frequent outbreaks of Herpes Simplex Virus defined as 4 or more episodes per year.
- 10) Subject has any history of eyebrow tattooing, or microblading that in the opinion of the investigator would interfere with the assessment of safety or efficacy.
- 11) Subject has used any semi-permanent eyebrow coloring (*e.g.*, tinting, dying, etc.) within 6 months prior to Visit 1 that in the opinion of the investigator would interfere with the assessment of safety or efficacy.

CONFIDENTIAL  
Page 9 of 57

12) Clinically significant laboratory abnormalities at Screening that, in the opinion of the Investigator, would make the subject a poor candidate for the study.

13) Subjects with absolute neutrophil count  $<1,000/\text{mm}^3$ , or platelet count  $<50,000/\text{ml}$ .

14) Subject used any of the following therapies within the specified period prior to Visit 1:

Systemic therapies:

- Disease Modifying Anti-Rheumatic Drugs (DMARDs), Biologics or immunosuppressants, such as: anakinra, adalimumab, azathioprine, glucocorticosteroids, cyclosporine, etanercept, infliximab, methotrexate, TNF inhibitors, ustekinumab, secukinumab, ixekizumab, certolizumab pegol: 4 weeks or 5 half-lives whichever is longer
- Oral retinoids: 12 weeks
- Plaquenil: 8 weeks
- JAK inhibitors (oral or topical): 1 year
- Intralesional steroids on the eyebrow area: 4 weeks

Topical therapies on the eyebrow area:

- Phototherapy, Laser Therapy: 12 weeks
- Anthralin, bimatoprost, glucocorticosteroids, diphenycprone, diphenylcycloprophenone (DPCP), Squaric acid dibutyl ester (SADBE), minoxidil, pimecrolimus, tacrolimus: 4 weeks
- Topical treatments (prescription and over-the-counter) that contain retinoids, retinol, alpha hydroxy acids (e.g. glycolic, lactic acids) and beta hydroxy acids (e.g. salicylic acid) on and around the eyebrow area: 4 weeks

15) Subject has a history of sensitivity to any of the ingredients in the study medication.

16) Subject has participated in an investigational drug or device trial in which administration of an investigational study drug or device occurred within 30 days or 5 half-lives (whichever is longer) prior to Visit 1. Subjects who have participated in a study of an investigational drug, device or biologic agent for alopecia areata (AA, AU or AT) within 1 year of screening will be eligible to participate only with individual permission from the Medical Monitor.

17) History of or current alcohol or drug abuse within 2 years of assessment for study enrollment.

18) Screening ECG findings of:

- QTcF  $>450\text{msec}$  for males or  $>470\text{msec}$  for females (use of the ECG algorithm is acceptable for this purpose)
- Heart rate  $<45$  or  $>100$  beats/minutes (inclusive)
- Rhythm disturbance other than sinus arrhythmia or ectopic supraventricular rhythm (ectopic atrial rhythm)
- Conduction disturbance including PR  $>240\text{msec}$ , pre-excitation (delta wave and PR  $<120\text{msec}$ ), second degree or higher AV block
- Acute or chronic signs of ischemia
- Left Bundle Branch Block
- Prior myocardial infarction

**Criteria for Evaluation:***Efficacy:*

The investigator will evaluate the severity of eyebrow loss using the Clinician's Eyebrow Assessment. Subjects will evaluate the severity of eyebrow loss using the Subject's Eyebrow Assessment.

*Safety:*

The investigator will assess clinical laboratory safety tests, vital sign readings, concomitant therapies, urine pregnancy test results, and adverse event (AE) information throughout the study.

*Other:*

Subjects will assess their satisfaction with the status of each eyebrow using the Subject Eyebrow Satisfaction scale. Standardized color photographs to assist with documenting the status of the subject's eyebrows will be taken throughout the study.

**Study Drug Administration:**

Subjects will apply ATI-50002 Topical Solution 0.46% BID for 24 weeks to the affected eyebrow(s). At Visit 2 (Baseline), after confirmation of the inclusion and exclusion criteria, an investigational staff member will instruct the subject on the proper study medication application technique, observe the first study medication application and monitor the subject for at least 20 minutes after the application. The subject will then start a 24-week treatment period.

**Statistical Methods:**

Summary descriptive statistics (N, mean, median, SD) by visit will be provided for all safety and efficacy parameters. Primary and secondary efficacy parameters are described below:

Mean change from baseline in eyebrow growth will be calculated as the mean change in the Clinician's Eyebrow Assessment (CEA) from Visit 2 (Baseline) compared to end of treatment (Visit 10). The CEA evaluates eyebrows on a scale from "No eyebrow hair" (grade 0) to "Full eyebrow hair" (grade 4).

Mean change from baseline in the Subject's Eyebrow Assessment (SEA) will be calculated from Visit 2 (Baseline) to end of treatment (Visit 10).

Mean change from baseline in the Subject's Eyebrow Satisfaction (SES) will be calculated from Visit 2 (Baseline) to end of treatment (Visit 10).

All efficacy summaries will be based on the per-protocol population including all subjects who have Baseline (Visit 2) and Visit 10 efficacy data and no major protocol violations.

Safety analyses will include descriptive statistics calculated on the safety parameters using the safety population. The proportion of subjects with treatment-emergent adverse events will be tabulated and presented by Medical Dictionary for Regulatory Activities (MedDRA) System Organ Class. Vital signs and clinically significant abnormal laboratory results will also be

tabulated and presented. Change from Baseline in the Local Tolerability Assessments (LTA) to end of treatment (Visit 10) will be summarized.

Data from all enrolled and treated subjects will be presented and summarized. Safety summaries will include listings of adverse events incidences within each MedDRA System Organ Class, and changes from pre-application values in vital signs. Adverse event summaries will be presented by study medication showing the proportion of subjects experiencing adverse events, both overall and by MedDRA System Organ Class.

CONFIDENTIAL  
Page 12 of 57

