## **6.9. Blinding**

### **6.9.1. Verification of blinding**

This study uses an open-label design.

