#### Screening Tests Only

Virology (HepB, HCV, HIV)  
 Total Iron Binding Capacity (TIBC)  
 Serum Iron

Serum Ferritin  
T3/T4, TSH  
Quantiferon  
Serum Pregnancy (Visit 1 only)

The results of the clinical laboratory tests will be reported on the laboratory's standard reports. The investigator must review all laboratory reports in a timely manner and note NCS or CS to define the clinical significance of any result that is outside the normal range for the laboratory. The investigator must date and initial every laboratory report.

The investigator must review the Visit 1 laboratory results for all the required analytes for each subject prior to Visit 2. The subject must not continue in the study and apply study medication if at Visit 2 any of the Visit 1 results are outside normal range for the laboratory AND, in the opinion of the investigator, CS.

The investigator must report all laboratory results that are BOTH outside the normal range for the laboratory AND, in the opinion of the investigator, CS as medical history if found prior to the first study medication application or as an AE if found after the first study medication application begins.

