## 8.2.4. Study Medication Interruption and Discontinuation

### 8.2.4.1 Study Medication Interruption

Treatment with ATI-50002 Topical Solution should be temporarily interrupted in the event of severe adverse events considered related to ATI-50002, or in the event of one or more of the abnormal laboratory values in Table 1.

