**Table 1: Study Medication Interruption Criteria**

Laboratory Test	Interrupt Study Medication if:	Resume Study Medication if:
WBC count	< 2 x 10  /L	≥ 2.5 x 10  /L
ANC	< 1 x 10  /L	≥ 1.5 x 10  /L
Lymphocyte count	< 0.5 x 10  /L	≥ 0.75 x 10  /L
Platelet count	< 75 x 10  /L	≥ 100 x 10  /L
Hemoglobin	< 8 g/dL or decrease > 2 g/dL	≥ 10 g/dL
AST or ALT	> 3 x ULN	< 2 x ULN or within 20% of baseline values
Serum creatinine	>2 x ULN	<1.5 x ULN or within 10% of baseline value

If a subject has one or more of the abnormal laboratory values noted in Table 1, the investigator or designee upon receipt and review of the central laboratory report should instruct the subject to interrupt study medication applications. The investigator or designee should ask the subject about symptoms, concomitant illnesses and medications and repeat the test(s) as soon as possible. The Medical Monitor must be notified of dose interruptions due to SAEs considered related to study medication or laboratory abnormalities noted in Table 1.

If the retest confirms the abnormal laboratory value, then the study medication interruption should continue, followed by repeat testing once a week or sooner at the discretion of the investigator. The subject should be followed until the laboratory abnormality(s) return to normal or to baseline values. Application of study medication may be resumed upon resolution of the abnormal laboratory values to the levels specified in Table 1 above.

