### **8.2.4.2 Study Medication Discontinuation**

Study medication should be permanently discontinued in the event of any of the following:

- Severe infection requiring parenteral antimicrobial therapy or hospitalization
- Symptomatic herpes zoster
- Malignancy – except for non-melanoma skin cancer (e.g., squamous or basal cell carcinoma) not in or near the treatment area
- Anaphylactic or severe allergic reaction
- WBC Count:  $< 1 \times 10^9/L$  or second occurrence of  $< 2 \times 10^9/L$
- ANC:  $< 0.5 \times 10^9/L$  or second occurrence of  $< 1 \times 10^9/L$
- Lymphocyte count:  $< 0.3 \times 10^9/L$  or second occurrence of  $< 0.5 \times 10^9/L$
- Platelet count:  $< 50 \times 10^9/L$  or second event of  $< 75 \times 10^9/L$  - in each case, value should be confirmed by retesting before treatment discontinuation
- Hemoglobin:  $< 6.5 \text{ g/dL}$  or second occurrence of  $< 8 \text{ g/dL}$  - in each case, value should be confirmed by retesting before treatment discontinuation
- AST or ALT:
  - $> 5 \times \text{ULN}$  persisting for 1 week of study medication interruption or second event of  $> 5 \times \text{ULN}$
  - $> 3 \times \text{ULN}$  with total bilirubin  $> 2 \times \text{ULN}$  or symptoms of hepatocellular injury [fatigue, nausea, vomiting, right upper quadrant pain or tenderness, fever, rash and/ or eosinophilia ( $> 5\%$ )].
- Serum creatinine:  $> 2 \times \text{ULN}$  persisting for  $> 2$  weeks of treatment discontinuation or second occurrence of  $> 2 \times \text{ULN}$

The continued treatment of subjects who experience other serious or severe adverse events considered related to study treatment should be discussed with the Sponsor's medical monitor.

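### Abnormal laboratory results are counted only when the investigator grades them clinically significant, so the planned counts can omit subjects who met the protocol's own numeric limits

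*Combined protocol and SAP*

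**What the plan says.** **The abnormality table.** The Statistical Methods text in the Synopsis (Section 1), repeated in Section 10.1, states: "Vital signs and clinically significant abnormal laboratory results will also be" tabulated. The restriction to clinically significant results applies to the laboratory data. Vital signs in the same sentence carry no such filter.

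**Who grades.** Section 7.2.4, under the screening tests, requires the investigator to "note NCS or CS to define the clinical significance of any result that is outside the normal range for the laboratory" (CS is clinically significant, NCS is not).

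**When a result becomes an adverse event.** The same section requires reporting of results that are "BOTH outside the normal range for the laboratory AND, in the opinion of the investigator, CS". After the first application these are reported as adverse events.

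**Other laboratory summaries.** Both statistical sections promise: "Summary descriptive statistics (N, mean, median, SD) by visit will be provided for all safety and efficacy parameters". There is no CS filter here, but also no minimum, maximum, shift table or count. Changes from pre-application values are promised for vital signs, and change from baseline for local tolerability. Neither is promised for laboratory values.

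**Numeric limits.** Section 8.2.4.1 calls for interruption in the event of severe related adverse events, "or in the event of one or more of the abnormal laboratory values in Table 1". Table 1 has seven laboratory rows: WBC, ANC, lymphocytes, platelets, hemoglobin, AST or ALT, and creatinine. Section 8.2.4.2 opens with "Study medication should be permanently discontinued in the event of any of the following" and gives a second set of cut-offs for the same tests. None of these limits refers to the CS/NCS grade.

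**The concern.** The numeric limits and the abnormality table do not meet anywhere in the analysis plan. The protocol regards certain laboratory values as serious enough to act on, yet the report need not say how many subjects had them. Nothing in the documents requires a value that meets a Table 1 or 8.2.4.2 limit to be graded CS. If it is graded NCS, it is absent from the abnormality table and is not reported as a laboratory adverse event.

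Safety comes first in the stated objective (Section 4), and there is no control arm, so individual excursions are most of the laboratory evidence that about 12 subjects can give. Section 3.1 shows how such wording reads in practice. It describes a Phase 1 study of the oral prodrug in which three subjects had mildly raised ALT or AST that were considered not clinically significant. It then reports that no clinically significant laboratory abnormality was seen. Under a CS-only table those three subjects would count as zero. The text does not say that they met any of the present limits.

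**Working it through.** The plan gives no figure to reproduce, and Section 10.2 says that no formal power calculation will be done. The check is a comparison of the passages, followed by illustrations with assumed values.

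**1. Which planned outputs would show a value that meets a limit but is graded NCS?**

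- Table of CS abnormal results (Sections 1 and 10.1): no, by definition.
- Adverse event tables: no, because Section 7.2.4 requires a CS grade for a laboratory result to be reported.
- By-visit N, mean, median and SD: the value is included, but it cannot be read off as a count.
- Count of subjects meeting a Table 1 or 8.2.4.2 limit: not planned.
- Shift against the normal range, or minimum and maximum: not planned.

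**2. Can the by-visit summary stand in for a count?** Assumed values: N = 12, eleven subjects with ALT at 0.5 x ULN and one at 3.1 x ULN, which is above the 3 x ULN interruption limit in Table 1.

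- Mean = (11 × 0.5 + 3.1)/12 = 8.6/12 = 0.72 x ULN.
- Median = 0.50 x ULN.
- SD = √{[11 × (0.5 − 0.717)² + (3.1 − 0.717)²]/11} = √(6.197/11) = 0.75 x ULN.

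Mean and median look normal. The SD suggests an outlier but does not say how many subjects met the limit. If the value is graded NCS, the abnormality table shows 0/12. A count that ignores the grade shows 1/12 = 8.3% (exact 95% interval 0.2% to 38.5%).

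**3. How much could the filter matter?** Let p be the share of subjects who meet a limit and c the chance that such a value is graded CS. The documents give neither, so both are assumed. With independent subjects, the chance that at least one appears in the table is 1 − (1 − p·c)^12.

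| p | c = 1 (grade ignored) | c = 0.5 | c = 0.25 |
|---|---|---|---|
| 5% | 0.46 | 0.26 | 0.14 |
| 10% | 0.72 | 0.46 | 0.26 |
| 20% | 0.93 | 0.72 | 0.46 |

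At p = 10% the expected number of subjects shown is 12 × 0.10 × c: 1.2, 0.6 and 0.3 across the columns. If investigators grade every such value CS (c = 1), nothing is lost.

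**4. Why shifts as well as limit counts?** Suppose platelets fall from 220 to 90 × 10⁹/L (assumed). That meets neither the Table 1 limit (< 75) nor the 8.2.4.2 limit (< 50), so a limit count correctly leaves it out. Only a shift table or a minimum would display the fall.

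**The case against.** **Other routes exist.** A reader might infer that one judgement controls every way in which a laboratory signal can surface. The documents do not support that. The by-visit summaries carry no CS filter. The limits act independently of the grade: a Table 1 value should lead to interruption and retest, and the Medical Monitor must be told of the interruption. Application modifications go on an eCRF (Section 6.6.8), reasons for withdrawal are recorded (Section 5.6), and an independent safety monitor reviews the data monthly (Section 7.2). All of this stands. It protects subjects during the trial and means that the records should exist. It does not commit the report to a count.

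**General wording.** Section 10.1 also promises that data from all treated subjects will be presented and summarized. This could cover an individual laboratory listing, which would be practical with about 12 subjects. It names no such listing and no count.

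**Open label.** Section 6.9.1 says "This study uses an open-label design", and a reader might infer that unmasked grading biases the safety comparison. With a single arm there is no between-arm comparison to bias. What remains is under-counting, or inconsistent grading across up to two sites.

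**All safety counts.** The point does not extend to vital signs, local tolerability or non-laboratory adverse events. Only laboratory counts pass through this filter.

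**SD of change.** In the platelet illustration, with the other eleven subjects unchanged, the mean change is −130/12 = −10.8 and the SD of change is 130/√12 = 37.5, which would draw attention. However, laboratory change from baseline is not among the stated summaries, and spread between subjects would blur the effect in raw by-visit values.

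**Noise.** Section 7.2.4 lists about 36 numeric analytes (differential counted as percentage and absolute), with three post-baseline laboratory visits (7, 10 and 11). If 5% of healthy values fall outside range (assumed), chance alone gives about 36 × 12 × 3 × 0.05 = 65 flagged results. This is a real drawback of shift tables, though not of counts against the protocol's limits.

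**Conclusion.** The point holds for laboratory abnormality counts. The only planned tabulation of abnormal laboratory results, and the route from a laboratory value to an adverse event, both depend on the investigator's grade. No planned output counts subjects who met the numeric limits in Table 1 or Section 8.2.4.2. A subject could meet such a limit and be absent from every planned count, although the value would still enter the by-visit summaries and should leave a trail in the conduct records.

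The size cannot be fixed from the documents, because it depends on how often limits are met and how such values are graded. Under the assumed ranges above, the chance that the table shows at least one such subject falls from 0.46–0.93 with the grade ignored to 0.14–0.46 when a quarter are graded CS. No hypothesis test or decision rule rests on this table, and the study is a descriptive pilot. This is a cheap improvement to reporting, not a flaw that undermines the trial.

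**What to change.** In Section 10.1, and in the matching Synopsis text, add the following for all treated subjects, regardless of the CS/NCS grade:

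1. The number of subjects with any post-baseline value, scheduled or repeat, meeting each numeric laboratory limit in Table 1 and Section 8.2.4.2. Some 8.2.4.2 criteria also require a second occurrence, persistence or symptoms. State for each whether the count uses the numeric part alone or the full criterion.
2. Minimum and maximum in the by-visit laboratory summaries.
3. Low/normal/high shifts from Visit 2 to each later laboratory visit, against the laboratory's normal range.
4. The CS grade as an extra column, so that the present table is kept.

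The values are already collected, no sampling is added, and no interruption or discontinuation rule changes. The cost is one or two more tables and some out-of-range flags expected by chance. Putting the limit counts first and the shift table second would keep those flags from obscuring the values that the protocol itself singles out.
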